8.3.2 Secondary Efficacy Analysis

[figure not shown]
The following analyses will be carried out on all three analysis populations defined above.:

- ACTitouch® treated subjects will be compared with multi-layer bandaging treated subjects in terms of the difference in changes in HRQOL at 16 weeks assessed by the overall score of the Charing Cross Venous Ulcer Questionnaire using a similar ANCOVA model as used in similar to the Primary Endpoint Analysis. If the primary efficacy analysis was significant, then the difference will be tested at the two-sided $\alpha=0.05$ level – Table 14.2.6.

8.3.3 Exploratory Efficacy Analysis

- To compare the difference in ulcer-free days at 16 weeks between ACTitouch® treated subjects with multi-layer bandaging treated subjects based on non-parametric analysis of covariance using the same covariates -Table 14.2.7.
- To compare the difference in changes in HRQOL at 16 weeks compared to baseline between ACTitouch® treated subjects with multi-layer bandaging treated subjects using the overall score of the VCSS and the same method as the Primary Endpoint Analysis -Table 14.2.10
- To compare the difference in the time-to-100% healed VLU between ACTitouch® treated subjects with multi-layer bandages treated subjects using a Cox Proportional Hazard model with the same covariates as above -Table 14.2.12.
- To compare the cumulative incidence graphs of subjects with 100% percent healed VLU between ACTitouch® treated subjects with multi-layer bandaging treated subjects using Kaplan-Meier product-moment estimates and the log rank test for differences in survival curves - Figure 1.

Accepted: _____

Date: _____

8 Oct 2017

Name: [name], Director of Clinical Resources and Research, Tactile Medical

TACTILE TABLES - SAP

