## 12.0 Data Analysis and Statistical Considerations

### 12.1 Statistical Considerations:

This is a prospective, randomized, stratified, open label, parallel-group, multi-center trial designed to assess the clinical non-inferiority with respect to the percentage of wound area reduction at 16 weeks with the ACTitouch® Adaptive Compression System compared to the Multi-layer Bandaging system in subjects with venous leg ulcer (VLU). Secondary endpoints include health-related quality of life (HRQOL) and Cost of the ACTitouch® Adaptive Compression System compared to the Multi-layer Bandaging system in subjects with VLU. Two hundred and four (204) subjects will be randomized 1:1 into 2 arms, ACTitouch® and Multi-layer Bandaging Systems. Subjects will receive follow-up evaluations at regularly scheduled clinic visits during 16 weeks of follow-up. Subjects will be randomized to 4 strata based on ulcer size and duration (age):

- Size of Ulcer
  - $1.5\text{cm} \leq \text{size} \leq 12\text{cm}$
  - $12\text{cm} < \text{size} \leq 50\text{cm}$
- Age of Ulcer
  - $1 \leq \text{age} \leq 6$  months
  - $6 < \text{age} \leq 24$  months

Subjects will be randomized to treatment groups within strata using a web-based randomization process.

Unless otherwise specified, all safety data, efficacy data, demographic data, and other baseline characteristics will be summarized by treatment group. Continuous data will be summarized by reporting the number of observations, mean, standard deviation, median, minimum and maximum values. Categorical data will be described using frequency tables showing the number and percentage of subjects falling within a particular category.

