Efficacy analysis and associated p-value calculation are described below and will be further elaborated in the Statistical Analysis Plan (SAP) issued prior to database lock. Statistical tests will be performed at a one-sided alpha of .025 for non-inferiority and two-sided alpha level of 0.05 for all other comparisons, unless otherwise specified. Between-group analyses will employ analysis of covariance (ANCOVA) with stratum and treatment group as covariates for continuous data, and chi-square or Cochran-Mantel Haenzel (CMH) methods for stratified categorical data. Kruskal-Wallis tests will be used to compare ordinal variables stratified by ulcer age, wound area and treatment group. If serious departures in the assumptions of normality and homogeneity of variance occur, nonparametric methods will be used for continuous data.

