#### 12.6 Analysis Plan:

##### 12.6.1 General Analysis Issues:

Statistical analysis will be performed using SAS Version 9.4 or higher. Non-inferiority analyses will be considered statistically significant at the

one-sided  $\alpha=.025$  level. All other p-values presented will be two-sided and will be considered statistically significant at the two-sided  $\alpha=.05$  level of significance unless otherwise noted. Statistical testing of the primary and secondary endpoints (Stage I) will be performed in hierarchical fashion. The primary efficacy analysis will be performed at the one-sided  $\alpha=.025$  level. If the primary efficacy analysis is statistically significant then the first secondary end point will be analyzed at the two-sided  $\alpha=.05$  level. If this analysis is statistically significant, then the second secondary end point will be analyzed at the two-sided  $\alpha=.05$  level. Otherwise, testing on secondary endpoints will cease and the treatment will not be considered beneficial on either secondary endpoint. P-values for exploratory endpoints will not be adjusted for multiple comparisons.

Baseline demographic and background variables will be summarized by treatment group and strata. For categorical variables, frequencies and percentages will be presented. For continuous variables, descriptive statistics including: sample size, mean, standard deviation, minimum, and maximum, will be presented. Continuous variables will be compared between treatment and control groups using ANCOVA. Categorical variables will be compared between treatment and control groups using the Kruskal-Wallis tests.

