Ulcer-related AE	Treatment N(%)	Control N(%)	p-value ^a
Ulcer infections	xx/xx(xxx.x%)	xx/xx(xxx.x%)	x.xxx
Ulcer maceration	xx/xx(xxx.x%)	xx/xx(xxx.x%)	x.xxx
Allergic reactions	xx/xx(xxx.x%)	xx/xx(xxx.x%)	x.xxx
Hospitalization for worsening VLU	xx/xx(xxx.x%)	xx/xx(xxx.x%)	x.xxx
All Ulcer-related AEs	xx/xx(xxx.x%)	xx/xx(xxx.x%)	x.xxx

Note: P-value calculated using the CMH test adjusting for ulcer size and duration (stratification)

TACTILE TABLES - SAP

Sponsor: Tactile Medical Systems
Protocol: 6010

page 1 of Y

Table 14.2.3 Primary Efficacy Analysis: Changes in % Wound Area Reduction
Evaluable Available Case Population

Label	Statistic	% Wound Area Reduction at Follow-up		Changes in % Wound Area Reduction from Baseline		[Treatment - Control] Difference (95% CI) [§]	P-Value [£]
		Treatment Group (N=122)	Control Group (N=128)	Treatment Group	Control Group		
baseline	N	xx	xx				
	Mean(SD)	xx.x(xx.x)	xx.x(xx.x)				
	Median(Min,Max)	xx(xx,xx)	xx(xx,xx)				
16 weeks	N	xx	xx	xx	xx		
	Mean(SD)	xx.x(xx.x)	xx.x(xx.x)	xx.x(xx.x)	xx.x(xx.x)	xx.x(xx.x, xx.x) [§]	x.xxx [£]
	Median(Min,Max)	xx(xx,xx)	xx(xx,xx)	xx(xx,xx)	xx(xx,xx)		

NOTES:[§] Estimates of mean difference between treatment groups, 95% confidence interval and P-value based on a linear mixed model ANCOVA with the following covariates: treatment group; duration of VLU ([1,6]; (6,24] months); baseline size of VLU, [1.5,12cm], (12,50cm); history of diabetes; age. [£] The covariate adjusted one-sided lower bound 97.5% confidence interval of the treatment difference in mean percent ulcer area reduction (calculated as mean of ACTitouch® group minus mean of multi-layer bandaging treated group) is compared to the non-inferiority margin (-.125) . If the lower bound exceeds the margin, the null hypothesis is rejected, and ACTitouch® system is deemed non-inferior to multi-layer bandaging[£].

TACTILE TABLES - SAP

Sponsor: Tactile Medical Systems
Protocol: 6010

page 1 of Y

Table 14.2.6 Secondary Efficacy Analysis: Changes in Charing Cross Scores at 16 Weeks
Evaluable Available Case Population

Label	Statistic	% Wound Area at Follow-up		Changes in % Wound Area from Baseline		[Treatment - Control] Difference (95% CI) [‡]	P-Value [‡]
		Treatment Group (N=122)	Control Group (N=128)	Treatment Group	Control Group		
baseline	N	xx	xx				
	Mean(SD)	xx.x(xx.x)	xx.x(xx.x)				
	Median(Min,Max)	xx(xx,xx)	xx(xx,xx)				
16 weeks	N	xx	xx	xx	xx		
	Mean(SD)	xx.x(xx.x)	xx.x(xx.x)	xx.x(xx.x)	xx.x(xx.x)	xx.x(xx.x, xx.x)	x.xxx

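### The Figure 1 log-rank test for time to healing names no strata although randomization is stratified by ulcer size and duration: a minor, nearly free improvement to an exploratory analysis

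*SAP*

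**What the plan says.** SAP 8.3.3 compares the curves of complete healing with "Kaplan-Meier product-moment estimates and the log rank test for differences in survival curves - Figure 1". No strata or covariates are named. Protocol 12.6.4 planned the Kaplan-Meier comparison only, so the log-rank test is an addition made in the SAP.

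On the design, Protocol 12.1 states: "Subjects will be randomized to 4 strata based on ulcer size and duration (age"), with size cut at 12 and duration cut at 6 months. It continues: "Subjects will be randomized to treatment groups within strata using a web-based randomization process".

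Elsewhere the plan carries these factors into its tests:

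- Protocol 12.1 puts stratum into the ANCOVA for continuous data and gives chi-square or CMH "methods for stratified categorical data". It gives no general rule for time-to-event data.
- In SAP 8.3 and its table shells, the models for percentage area reduction, Charing Cross score, ulcer-free days and VCSS all include size class and duration class.
- The Cox model for time to 100% healed, in the bullet just before Figure 1, uses the same covariates. Its shell has rows for ulcer size and ulcer duration.
- The footnotes to safety Tables 14.3.1 and 14.3.3 state that stratification is accounted for.

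Time to healing and cumulative incidence are exploratory endpoints (Protocol 12.3.3). They lie outside the testing hierarchy and have no multiplicity adjustment (Protocol 12.6.1).

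**The concern.** Randomizing within strata balances the arms on those factors by design. If the factors predict healing, the true variability of the treatment comparison is then smaller than the variance the ordinary log-rank test uses, so the test rejects too rarely under the null. Pooling strata with unlike healing rates also pulls the apparent hazard ratio toward 1. Both effects cost power, whichever arm heals faster.

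The direction matters here. The synopsis objective is a comparable rate of healing, and a non-significant log-rank result invites that reading. A test that under-detects a difference, including slower healing on ACTitouch, leans toward the conclusion the trial hopes to support. Figure 1 is also the one efficacy test in SAP 8.3 that drops the stratification factors.

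**Working it through.** The documents give no healing rate, event count, hazard ratio or power for time to healing, so there is no stated figure to reproduce. The consequence was checked by simulation.

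**Inputs from the documents**

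- Size and allocation: "Two hundred and four (204) subjects will be randomized 1:1 into 2 arms" (Protocol 12.1). The SAP shells print "Treatment Group (N=122") and "Control Group (N=128"), that is 122 + 128 = 250, so both totals were run.
- Four strata and 16 weeks of treatment.
- Sidedness: "All other p-values presented will be two-sided and will be considered statistically significant at the two-sided" 0.05 level (Protocol 12.6.1).

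**Assumptions not in the documents**

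- Equal strata and permuted blocks of 4 within stratum.
- Exponential healing times, observed continuously rather than at visits.
- Exponential dropout with cumulative hazard 0.163 over 16 weeks: 1 − exp(−0.163) = 15%.
- Average control healing of 40% or 60% at 16 weeks.
- Treatment hazard ratio (HR) 1.6.
- A prognostic HR *h* for each factor, giving stratum hazards in the ratio 1 : *h* : *h* : *h*². For *h* = 0.7, 0.5 and 0.33 the extreme strata differ by 1/*h*² = 2.0, 4.0 and 9.2 times.

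**Formulas.** At each healing, let p be the treated fraction of those still at risk and g = 1 if the healed subject is treated. Then U = Σ(g − p), V = Σp(1 − p) and Z = U/√V. The stratified test computes U and V within each stratum k and uses Z = ΣUₖ/√ΣVₖ.

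**Cross-check** (N = 204, 40% healing, *h* = 1). The 16-week healing hazards are −ln(0.60) = 0.511 for control and 1.6 × 0.511 = 0.817 for treatment. Allowing for dropout:

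- Control event probability: 0.511/0.674 × (1 − e^−0.674) = 0.372.
- Treatment event probability: 0.817/0.980 × (1 − e^−0.980) = 0.521.
- Expected events: 102 × 0.893 = 91.
- Schoenfeld power: Φ(½√91 × ln 1.6 − 1.96) = Φ(0.28) = 61%.

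The simulated power is 60%, which agrees.

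**Results, N = 204, 4,000 trials per setting (unstratified v stratified)**

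| Control healing | *h* | Type I error, % | Power at HR 1.6, % | Loss, points | Unstratified p larger (HR 1.6) |
|---|---|---|---|---|---|
| 40% | 1.0 | 5.1 v 5.0 | 60.3 v 59.7 | −0.6 | 43% |
| 40% | 0.7 | 5.4 v 5.9 | 58.9 v 59.7 | 0.8 | 56% |
| 40% | 0.5 | 3.9 v 4.6 | 55.9 v 60.8 | 4.9 | 74% |
| 40% | 0.33 | 3.0 v 5.0 | 47.1 v 60.6 | 13.5 | 86% |
| 60% | 1.0 | 5.6 v 5.4 | 76.7 v 76.5 | −0.2 | 40% |
| 60% | 0.7 | 5.0 v 5.5 | 74.4 v 76.2 | 1.8 | 62% |
| 60% | 0.5 | 4.3 v 6.0 | 68.0 v 75.0 | 7.0 | 80% |
| 60% | 0.33 | 2.1 v 4.4 | 57.6 v 75.6 | 18.0 | 90% |

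The simulation standard error near 5% is √(0.05 × 0.95/4000) = 0.34 points. The eight stratified type I errors average 5.2%, close to nominal.

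With N = 250, at 40% and 60% healing, the losses are 0.6 and 0.9 points for *h* = 0.7, 4.1 and 6.3 for *h* = 0.5, and 12.8 and 18.2 for *h* = 0.33. With *h* = 1 there is no loss.

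**Second check**, setting control healing by stratum directly (N = 204, 10% exits, 4,000 trials per setting):

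| Healing by stratum | Type I error, % | Power HR 1.5, % | Power HR 1.7, % | Power HR 0.67, % |
|---|---|---|---|---|
| 65/45/40/20% | 4.0 v 5.0 | 45 v 51 | 68 v 73 | 36 v 40 |
| 75/50/35/10% | 2.7 v 4.9 | 34 v 49 | 60 v 74 | 31 v 41 |

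In this check, with strata that are not prognostic, power at HR 1.5 is 52% v 51%.

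These are strong gradients. Hazards in the extreme strata differ by ln(0.35)/ln(0.80) = 4.7 times in the first row and ln(0.25)/ln(0.90) = 13 times in the second.

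**The case against.** The strongest reply is that the plan already has a stratum-adjusted test of this endpoint. The Cox model in the preceding bullet includes both stratification factors and reports a treatment p-value, so the log-rank test is a companion to a plot. No confirmatory decision rests on it, and a conservative test creates no excess of false positives. This stands, and it is why the point is minor. The SAP does not, however, say which of the two p-values takes precedence.

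A second reply is that *unstratified* is inferred from silence. The SAP calls itself abbreviated, no shell or footnote for Figure 1 is visible, and for Table 14.3.1 the stratification appears only in the footnote. This stands in part. The SAP does not use the word, but a log-rank test named without strata would ordinarily be programmed without them.

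A reader might infer that the Figure 1 p-value will be too large and that power will certainly be lost. The documents do not support that. They give no reason for choosing these strata and no healing rate by stratum. The loss vanishes if the strata do not predict healing, and even with a moderate gradient (*h* = 0.5) the unstratified p-value was the larger in only 74% to 80% of simulated trials. Nor can one infer that the plan's inference on healing ignores the strata, because the Cox model does not.

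Finally, stratifying will not make the two p-values agree, since the Cox model also adjusts for diabetes and age. A stratified p-value also does not strictly test the gap between the pooled curves drawn. Both remarks are correct, and the second is met by labelling.

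**Conclusion.** The point holds conditionally and is minor. As worded, the Figure 1 test omits the factors by which the trial randomizes and for which the other efficacy tests in SAP 8.3 adjust. To the extent that size and duration predict healing, it is conservative: type I error was 2.1% to 4.3% under moderate to steep gradients at N = 204.

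For faster healing on ACTitouch (HR 1.5 to 1.7) the power loss is nil with no gradient, about 1 to 2 points with a weak one, 5 to 7 with a moderate one and 14 to 18 with a steep one. For slower healing (HR 0.67) it was 4 and 10 points under the two gradients tried. All these sizes rest on assumed healing rates, equal strata and exponential healing times. Where the true trial lies in the range cannot be read from the documents. Nothing here affects the primary or secondary conclusions.

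**What to change.** In SAP 8.3.3, replace the log-rank wording for Figure 1 with: *the log-rank test stratified by the four randomization strata (ulcer size × ulcer duration)*, using the strata as defined in Protocol 12.1. Label the p-value on Figure 1 as stratified, so that it is not read as a test of the pooled curves.

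The cost is one phrase in the SAP and one STRATA term in the program. When the strata were not prognostic, stratifying cost less than 1 point of power in the main simulation at N = 204 and about 1 point (52% v 51%) in the second check. Some difference from the Cox p-value will remain and should be expected.

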APPENDIX: DATA TABLES

TACTILE TABLES - SAP

Sponsor: Tactile Medical Systems
Protocol: 6010

page 1 of x

Table 14.1.1 Patient Disposition

ITT sample

	1.5cm<=size<=12cm				12cm<size<= 50cm			
	1<=age<6 months		1<=age<6 months		6<=age<=24 months		6<=age<= 24 months	
	Treatment (N)	Control (N)	Treatment (N)	Control (N)	Treatment (N)	Control (N)	Treatment (N)	Control (N)
Randomized	xx/xx(xxx.x%)	xx/xx(xxx.x%)	xx/xx(xxx.x%)	xx/xx(xxx.x%)	xx/xx(xxx.x%)	xx/xx(xxx.x%)	xx/xx(xxx.x%)	xx/xx(xxx.x%)
Safety	xx/xx(xxx.x%)	xx/xx(xxx.x%)	xx/xx(xxx.x%)	xx/xx(xxx.x%)	xx/xx(xxx.x%)	xx/xx(xxx.x%)	xx/xx(xxx.x%)	xx/xx(xxx.x%)
Completed	xx/xx(xxx.x%)	xx/xx(xxx.x%)	xx/xx(xxx.x%)	xx/xx(xxx.x%)	xx/xx(xxx.x%)	xx/xx(xxx.x%)	xx/xx(xxx.x%)	xx/xx(xxx.x%)
Discontinued	xx/xx(xxx.x%)	xx/xx(xxx.x%)	xx/xx(xxx.x%)	xx/xx(xxx.x%)	xx/xx(xxx.x%)	xx/xx(xxx.x%)	xx/xx(xxx.x%)	xx/xx(xxx.x%)
Primary Reason for Discontinuation:								
Adverse Event	xx/xx(xxx.x%)	xx/xx(xxx.x%)	xx/xx(xxx.x%)	xx/xx(xxx.x%)	xx/xx(xxx.x%)	xx/xx(xxx.x%)	xx/xx(xxx.x%)	xx/xx(xxx.x%)
Protocol Violation	xx/xx(xxx.x%)	xx/xx(xxx.x%)	xx/xx(xxx.x%)	xx/xx(xxx.x%)	xx/xx(xxx.x%)	xx/xx(xxx.x%)	xx/xx(xxx.x%)	xx/xx(xxx.x%)
Lost to Follow-up	xx/xx(xxx.x%)	xx/xx(xxx.x%)	xx/xx(xxx.x%)	xx/xx(xxx.x%)	xx/xx(xxx.x%)	xx/xx(xxx.x%)	xx/xx(xxx.x%)	xx/xx(xxx.x%)
Other	xx/xx(xxx.x%)	xx/xx(xxx.x%)	xx/xx(xxx.x%)	xx/xx(xxx.x%)	xx/xx(xxx.x%)	xx/xx(xxx.x%)	xx/xx(xxx.x%)	xx/xx(xxx.x%)

TACTILE TABLES - SAP

Sponsor: Tactile Medical Systems
 Protocol: 6010

page 1 of x

Table 14.1.2 Patient Disposition By Site
 ITT sample

	Treatment N(%) ^b	Control N(%) ^b	Total N(%) ^b
xxxx	xx/xx(xxx.x%)	xx/xx(xxx.x%)	xx/xx(xxx.x%)
xxxx	xx/xx(xxx.x%)	xx/xx(xxx.x%)	xx/xx(xxx.x%)
xxxx	xx/xx(xxx.x%)	xx/xx(xxx.x%)	xx/xx(xxx.x%)
xxxx	xx/xx(xxx.x%)	xx/xx(xxx.x%)	xx/xx(xxx.x%)
xxxx	xx/xx(xxx.x%)	xx/xx(xxx.x%)	xx/xx(xxx.x%)

Note: denominator of all percentages is number randomized by group

TACTILE TABLES - SAP

Sponsor: Tactile Medical Systems
Protocol: 6010

page 1 of Y

Table 14.3.1 Safety Analysis: Summary Incidence of Adverse Events
Safety sample

Condition	Treatment N(%)	Control N(%)	P-value
Safety Analysis Set	xx	xx	
Patients with Adverse Events	xx(xxx.x%)	xx(xxx.x%)	x.xxx
Patients with AEs by Severity ^a			
No Event	xx(xxx.x%)	xx(xxx.x%)	x.xxx
Mild	xx(xxx.x%)	xx(xxx.x%)	
Moderate	xx(xxx.x%)	xx(xxx.x%)	
Severe	xx(xxx.x%)	xx(xxx.x%)	
Patients with AEs by Causality ^a			
Definitely related	xx(xxx.x%)	xx(xxx.x%)	x.xxx
Probably related	xx(xxx.x%)	xx(xxx.x%)	
Possibly related	xx(xxx.x%)	xx(xxx.x%)	
Not related	xx(xxx.x%)	xx(xxx.x%)	
No Event	xx(xxx.x%)	xx(xxx.x%)	
Outcome			
No Event	xx(xxx.x%)	xx(xxx.x%)	x.xxx
Resolved	xx(xxx.x%)	xx(xxx.x%)	
Resolved w/ sequelae	xx(xxx.x%)	xx(xxx.x%)	
Continuing	xx(xxx.x%)	xx(xxx.x%)	
Lost to follow-up	xx(xxx.x%)	xx(xxx.x%)	
Death	xx(xxx.x%)	xx(xxx.x%)	

TACTILE TABLES - SAP

Condition	Treatment N(%)	Control N(%)	P-value
Patients with SAEs	xx(xxx.x%)	xx(xxx.x%)	x.xxx
Patients Discontinued due to AE	xx(xxx.x%)	xx(xxx.x%)	x.xxx

NOTE: P-value based on Kruskal-Wallis test controlling for stratification. Denominator is the number of patients in the Safety Analysis Set.
^aPatients experiencing more than one adverse event are counted under the maximum severity experienced across events.

TACTILE TABLES - SAP

Sponsor: Tactile Medical Systems
 Protocol: 6010

page 1 of Y

Table 14.3.2 Safety Analysis: Incidence of Adverse Events by Internal AE Code
 Safety sample

Internal AE Code	Treatment N(%)	Control N(%)	p-value ^a
Patients with Adverse Events	xx(xxx.x%)	xx(xxx.x%)	xxxx
AE_CODE XX	xx(xxx.x%)	xx(xxx.x%)	x.xxx
AE_CODE XX	xx(xxx.x%)	xx(xxx.x%)	x.xxx
AE_CODE XX	xx(xxx.x%)	xx(xxx.x%)	x.xxx
AE_CODE XX	xx(xxx.x%)	xx(xxx.x%)	x.xxx
AE_CODE XX	xx(xxx.x%)	xx(xxx.x%)	x.xxx
AE_CODE XX	xx(xxx.x%)	xx(xxx.x%)	x.xxx
AE_CODE XX	xx(xxx.x%)	xx(xxx.x%)	x.xxx
AE_CODE XX	xx(xxx.x%)	xx(xxx.x%)	x.xxx
AE_CODE XX	xx(xxx.x%)	xx(xxx.x%)	x.xxx
AE_CODE XX	xx(xxx.x%)	xx(xxx.x%)	x.xxx

Note: A patient experiencing multiple incidences of an event with the same internal AE code is counted only once.
^a P-value calculated from CMH Test.

TACTILE TABLES - SAP

Sponsor: Tactile Medical Systems
 Protocol: 6010

page 1 of Y

Table 16.2.7.1 Listing of Adverse Events
 Safety sample

Treatment Group	Patient ID	Onset Date (Study Day)	Stop Date (Study Day)	Internal AE Code	Serious	Duration	Severity	Causality	Outcome
xxx	xx	ddmmyy (xx)	ddmmyy(xx)	xx	xx	xx	xx	xx	xx
xxx	xx	ddmmyy (xx)	ddmmyy(xx)	xx	xx	xx	xx	xx	xx
xxx	xx	ddmmyy(xx)	ddmmyy(xx)	xx	xx	xx	xx	xx	xx
xxx	xx	ddmmyy(xx)	ddmmyy(xx)	xx	xx	xx	xx	xx	xx
xxx	xx	ddmmyy(xx)	ddmmyy(xx)	xx	xx	xx	xx	xx	xx
xxx	xx	ddmmyy(xx)	ddmmyy(xx)	xx	xx	xx	xx	xx	xx
xxx	xx	ddmmyy(xx)	ddmmyy(xx)	xx	xx	xx	xx	xx	xx
xxx	xx	ddmmyy(xx)	ddmmyy(xx)	xx	xx	xx	xx	xx	xx
xxx	xx	ddmmyy(xx)	ddmmyy(xx)	xx	xx	xx	xx	xx	xx

TACTILE TABLES - SAP

Sponsor: Tactile Medical Systems
Protocol: 6010

page 1 of Y

Table 14.3.3 Safety Analysis: Incidence of Ulcer-Related Adverse Events at 16 Weeks
Safety sample

Ulcer-related AE	Treatment N(%)	Control N(%)	p-value ^a
Ulcer infections	xx/xx(xxx.x%)	xx/xx(xxx.x%)	x.xxx
Ulcer maceration	xx/xx(xxx.x%)	xx/xx(xxx.x%)	x.xxx
Allergic reactions	xx/xx(xxx.x%)	xx/xx(xxx.x%)	x.xxx
Hospitalization for worsening VLU	xx/xx(xxx.x%)	xx/xx(xxx.x%)	x.xxx
All Ulcer-related AEs	xx/xx(xxx.x%)	xx/xx(xxx.x%)	x.xxx

Note: P-value calculated using the CMH test adjusting for ulcer size and duration (stratification)

TACTILE TABLES - SAP

Sponsor: Tactile Medical Systems
Protocol: 6010

page 1 of Y

Table 14.2.3 Primary Efficacy Analysis: Changes in % Wound Area Reduction
Evaluable Available Case Population

Label	Statistic	% Wound Area Reduction at Follow-up		Changes in % Wound Area Reduction from Baseline		[Treatment - Control] Difference (95% CI) [§]	P-Value [£]
		Treatment Group (N=122)	Control Group (N=128)	Treatment Group	Control Group		
baseline	N	xx	xx				
	Mean(SD)	xx.x(xx.x)	xx.x(xx.x)				
	Median(Min,Max)	xx(xx,xx)	xx(xx,xx)				
16 weeks	N	xx	xx	xx	xx		
	Mean(SD)	xx.x(xx.x)	xx.x(xx.x)	xx.x(xx.x)	xx.x(xx.x)	xx.x(xx.x, xx.x) [§]	x.xxx [£]
	Median(Min,Max)	xx(xx,xx)	xx(xx,xx)	xx(xx,xx)	xx(xx,xx)		

NOTES:[§] Estimates of mean difference between treatment groups, 95% confidence interval and P-value based on a linear mixed model ANCOVA with the following covariates: treatment group; duration of VLU ([1,6]; (6,24] months); baseline size of VLU, [1.5,12cm], (12,50cm); history of diabetes; age. [£] The covariate adjusted one-sided lower bound 97.5% confidence interval of the treatment difference in mean percent ulcer area reduction (calculated as mean of ACTitouch® group minus mean of multi-layer bandaging treated group) is compared to the non-inferiority margin (-.125) . If the lower bound exceeds the margin, the null hypothesis is rejected, and ACTitouch® system is deemed non-inferior to multi-layer bandaging[£].

TACTILE TABLES - SAP

Sponsor: Tactile Medical Systems
Protocol: 6010

page 1 of Y

Table 14.2.6 Secondary Efficacy Analysis: Changes in Charing Cross Scores at 16 Weeks
Evaluable Available Case Population

Label	Statistic	% Wound Area at Follow-up		Changes in % Wound Area from Baseline		[Treatment - Control] Difference (95% CI) [‡]	P-Value [‡]
		Treatment Group (N=122)	Control Group (N=128)	Treatment Group	Control Group		
baseline	N	xx	xx				
	Mean(SD)	xx.x(xx.x)	xx.x(xx.x)				
	Median(Min,Max)	xx(xx,xx)	xx(xx,xx)				
16 weeks	N	xx	xx	xx	xx		
	Mean(SD)	xx.x(xx.x)	xx.x(xx.x)	xx.x(xx.x)	xx.x(xx.x)	xx.x(xx.x, xx.x)	x.xxx
	Median(Min,Max)	xx(xx,xx)	xx(xx,xx)	xx(xx,xx)	xx(xx,xx)		

Note: [‡]Estimates of mean difference between treatment groups, 95% confidence interval and P-value based on linear mixed model ANCOVA with the following covariates: treatment group; duration of VLU ([1,6]; (6,24] months); baseline size of VLU, [1.5,12cm], (12,50cm]; history of diabetes; age.

TACTILE TABLES - SAP

Sponsor: Tactile Medical Systems
Protocol: 6010

page 1 of Y

Table 14.2.7 Exploratory Efficacy Analysis: Ulcer Free Days at 16 Weeks
Evaluable Available Case Population

Label	Statistic	% Wound Area at Follow-up		Changes in % Wound Area from Baseline		[Treatment - Control] Difference (95% CI)*	P-Value*
		Treatment Group (N=122)	Control Group (N=128)	Treatment Group	Control Group		
baseline	N	xx	xx				
	Mean(SD)	xx.x(xx.x)	xx.x(xx.x)				
	Median(Min,Max)	xx(xx,xx)	xx(xx,xx)				
16 weeks	N	xx	xx	xx	xx		
	Mean(SD)	xx.x(xx.x)	xx.x(xx.x)	xx.x(xx.x)	xx.x(xx.x)	xx.x(xx.x, xx.x)	x.xxx
	Median(Min,Max)	xx(xx,xx)	xx(xx,xx)	xx(xx,xx)	xx(xx,xx)		

Note: *Estimates of mean difference between treatment groups, 95% confidence interval and P-value based on non-parametric ANCOVA with the following covariates: treatment group; duration of VLU ([1,6]; (6,24] months); baseline size of VLU, [1.5,12cm], (12,50cm]; history of diabetes; age.

TACTILE TABLES - SAP

Sponsor: Tactile Medical Systems
Protocol: 6010

page 1 of Y

Table 14.2.10 Exploratory Efficacy Analysis: Changes in VCSS at 16 Weeks
Evaluable Available Case Population

Label	Statistic	% Wound Area at Follow-up		Changes in % Wound Area from Baseline		[Treatment - Control] Difference (95% CI) [*]	P-Value [*]
		Treatment Group (N=122)	Control Group (N=128)	Treatment Group	Control Group		
baseline	N	xx	xx				
	Mean(SD)	xx.x(xx.x)	xx.x(xx.x)				
	Median(Min,Max)	xx(xx,xx)	xx(xx,xx)				
16 weeks	N	xx	xx	xx	xx		
	Mean(SD)	xx.x(xx.x)	xx.x(xx.x)	xx.x(xx.x)	xx.x(xx.x)	xx.x(xx.x, xx.x)	x.xxx
	Median(Min,Max)	xx(xx,xx)	xx(xx,xx)	xx(xx,xx)	xx(xx,xx)		

Note: ^{*}Estimates of mean difference between treatment groups, 95% confidence interval and P-value based on ANCOVA with the following covariates: treatment group; duration of VLU ([1,6]; (6,24] months); baseline size of VLU, [1.5,12cm], (12,50cm]; history of diabetes; age.

TACTILE TABLES - SAP

Sponsor: Tactile Medical Systems
 Protocol: 6010

page 1 of Y

Table 14.2.11. Exploratory Analysis: Cox PH Analysis of the Time to 100% Healed VLU

Variable	Hazard Rate	95% Confidence Interval		P-value
		Hazard Rate		
Treatment Group	x.xxx	(x.xxx, x.xxx)		x.xxx
Ulcer Size	x.xxx	(x.xxx, x.xxx)		x.xxx
Ulcer Duration	x.xxx	(x.xxx, x.xxx)		x.xxx
Diabetes	x.xxx	(x.xxx, x.xxx)		x.xxx
Age	x.xxx	(x.xxx, x.xxx)		x.xxx

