#### 12.6.5 Safety Endpoint Analysis

The following analyses will be carried out on the Safety Populations. ACTitouch® treated subjects will be compared with multi-layer bandaging treated subjects in terms of:

- the difference in the incidence of ulcer-related adverse events (defined as ulcer infections, maceration, allergic reaction to dressing, or hospitalization for worsening VLU) at 16 weeks using the Kruskal-Wallis test.
- the difference in the incidence of ulcer infections at 16 weeks using the Kruskal-Wallis test.
- the difference in the incidence of ulcer maceration at 16 weeks using the Kruskal-Wallis test.
- the difference in the incidence of allergic reactions to dressing at 16 weeks using the Kruskal-Wallis test.
- the difference in the incidence of hospitalization for worsening VLU at 16 weeks using the Kruskal-Wallis test.

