8.2.1 Adverse Events

Adverse events will be coded according to pre-specified Tactile internal codes. Adverse events will be summarized by severity, outcome, causality and seriousness (i.e., SAE) and stratified by treatment group (Table 14.3.1). For subjects with more than one event, the event with the highest level of severity, outcome or causality, seriousness, respectively, will be reported. The number and percentage of subjects with an event by the internal Tactile AE codes will be compared by treatment group (Tables 14.3.2). Subjects with more than one event by internal Tactile code will be counted only once. All AEs will be listed, sorted by treatment group, subject identification, and date of the AE (Table 16.2.7.1). Data presented will include: causality, severity, seriousness, outcome, verbatim description, internal Tactile codes.

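### Kruskal-Wallis is assigned to categorical variables with no defined order (AE outcome, any nominal baseline variable), and Table 14.3.1 does not name the stratified form it claims to use

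*SAP*

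**What the plan says.** **General rule.** Protocol 12.1 assigns "chi-square or Cochran-Mantel Haenzel (CMH) methods for stratified categorical data" and reserves Kruskal-Wallis for ordinal variables.

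**Baseline.** Protocol 12.6.1 states: "Categorical variables will be compared between treatment and control groups using the Kruskal-Wallis tests". It does not restrict this to ordinal variables.

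**Safety, protocol.** Protocol 12.6.5 lists five yes/no incidences (ulcer-related AEs overall and four components). Each is compared "using the Kruskal-Wallis test", with no mention of strata.

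**Safety, SAP.** One footnote covers every p-value in Table 14.3.1: "P-value based on Kruskal-Wallis test controlling for stratification". The rows under it are of three kinds:
- Yes/no: any AE, "Patients with SAEs", and discontinued due to AE.
- Ordered: "Patients with AEs by Severity" (no event to severe) and causality (definitely related to not related, then no event).
- Outcome: no event, resolved, "Resolved w/ sequelae", continuing, lost to follow-up, death. One p-value, no stated scores.

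SAP 8.2.1 says that for patients with several events "the event with the highest level of severity, outcome or causality, seriousness, respectively, will be reported". This treats outcome as ranked but gives no ranking. Tables 14.3.2 and 14.3.3 use CMH; the note to 14.3.3 adjusts for ulcer size and duration.

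**The concern.** There are three separate problems.

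1. **Order dependence.** Kruskal-Wallis ranks the category codes. If the categories have no agreed order, the p-value follows the coding. Lost to follow-up has no natural place between resolved and death. The same applies to any nominal baseline variable with three or more levels under 12.6.1.
2. **Unnamed stratified method.** The ordinary test has no strata. Two programmers could follow the 14.3.1 note and produce different results, one stratified and one not.
3. **Internal conflict.** 12.6.1 and 12.6.5 depart from 12.1, and the any-AE row is assigned Kruskal-Wallis in 14.3.1 and CMH in 14.3.2.

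At stake are the reproducibility and readability of the safety and baseline p-values.

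**Working it through.** The plan states no figure that depends on this choice, so there is none to reproduce. Arm sizes 122 and 128 are printed in the SAP efficacy table shells; 102 per arm is the protocol's planned number. The four strata (ulcer size by duration) come from Protocol 12.1. **All event counts and stratum rates below are assumptions.**

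**Step 1. Yes/no rows.** With two arms and a binary variable, H = (N − 1)/N × Pearson chi-square. For 40/122 against 28/128, chi-square = 3.756 (p = 0.0526) and H = 249/250 × 3.756 = 3.741 (p = 0.0531). The test is valid and does not depend on coding. It is simply unstratified.

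**Step 2. A stratified form exists.** The CMH row-mean-score test with rank scores gives 3.741 on the same data in one stratum, identical to Kruskal-Wallis, and it extends across strata. With modified ridit scores it is van Elteren's test.

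**Step 3. Does the choice matter?** Assumed strata (events/patients, treatment then control): 6/45 and 4/40; 10/32 and 8/38; 9/25 and 8/28; 15/20 and 14/22. Totals are 40/122 and 34/128; pooled stratum rates run from 10/85 = 12% to 29/42 = 69%.

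| Test | p |
|---|---|
| Ordinary Kruskal-Wallis | 0.282 |
| CMH row mean scores, rank scores | 0.177 |
| van Elteren (modified ridits) | 0.158 |
| Mantel-Haenszel (CMH), 4 strata | 0.158 |

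For Mantel-Haenszel, the sum of observed minus expected treatment events is 4.649 and the variance is 10.817, so the statistic is 4.649²/10.817 = 1.998. The two stratified rank forms differ from each other as well as from the ordinary test.

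A simulation (4,000 runs, 124 per arm, strata balanced, assumed stratum rates 10, 30, 40 and 70%) gave a rejection rate under no difference of 0.030 unstratified and 0.055 stratified. At an odds ratio of 1.8, power was 0.43 and 0.50. Ignoring strata is conservative here and loses some power.

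**Step 4. Outcome row.** Two sets of assumed counts, in the listed category order:
- Set A: 62, 34, 3, 17, 5, 1 (n = 122) against 70, 44, 2, 7, 4, 1 (n = 128).
- Set B: 60, 18, 6, 12, 5, 1 (n = 102) against 62, 26, 1, 10, 3, 0 (n = 102).

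| Category order used for Kruskal-Wallis | Set A, p | Set B, p |
|---|---|---|
| As listed in the shell | 0.232 | 0.464 |
| Alphabetical | 0.097 | 0.515 |
| Only lost to follow-up moved | 0.207 to 0.271 | 0.464 to 0.600 |
| No event first, death last, rest free | 0.207 to 0.994 | 0.370 to 0.997 |
| All 720 orders | 0.050 to 0.997 | 0.036 to 0.997 |
| Order-free chi-square, 5 df | 0.296 | 0.241 |

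Across all 720 orders, p falls below 0.05 in none for set A and in 24 for set B. With no event first and death last, it does so in neither set. The chi-square is itself approximate: in set B the expected counts per arm are 3.5, 4 and 0.5 in three of the six categories.

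Stratifying a rank test would not remove this dependence, because within each stratum it still ranks the codes.

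**Step 5. Same row, two tests.** The any-AE row in 14.3.1 and 14.3.2 has the same patients and the same Safety sample but two differently named tests. No assumed data are needed to see this.

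**The case against.** The best defence is that stratification is plainly intended. The 14.3.1 note says so, and Protocol 12.1 describes Kruskal-Wallis as stratified by ulcer age and wound area. Read that way, the yes/no rows would already be stratified. This stands to the extent that a reader might infer that these p-values ignore the randomization strata, and the documents do not establish that. They establish only that the method is unnamed. The 12.1 sentence does not settle it, because it also lists treatment group, the factor being compared, among the stratifiers.

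Three further points stand:
- Using the test on yes/no data is not an error (step 1), and 12.1 allows plain chi-square.
- Severity and causality are ordered, so a rank test suits them.
- SAP 8.2.3 and Table 14.3.3, dated October 2017 against the protocol's September 2016, already put the five incidences of 12.6.5 under CMH. The abbreviated SAP also has no baseline table shell, so 12.6.1 cannot be traced to a planned SAP output.

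For Outcome, the defence is that SAP 8.2.1 speaks of a highest level and the shell lists a sensible sequence. An order may be intended, so calling the p-value meaningless would go too far. It is undefined until the order is written down. The full 720-order range should not be read as the practical effect either, since it includes orders nobody would choose.

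**Conclusion.** The point holds as a specification defect of low severity. For Outcome, and for any nominal baseline variable with three or more levels, the plan prescribes a p-value that depends on an unstated category order. For Table 14.3.1 as a whole, control for strata holds only if an unnamed extension is used. The plan also contradicts its own rule in 12.1 and its own Tables 14.3.2 and 14.3.3.

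On the assumed counts, moving only lost to follow-up changes p modestly (0.21 to 0.27, or 0.46 to 0.60). Alphabetical coding moved it from 0.23 to 0.10 in one set and from 0.46 to 0.52 in the other. These sizes rest entirely on assumed data. The order dependence and the conflicts between sections do not.

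The documents do not support a reading that the yes/no p-values are invalid or certainly unstratified. No decision rule is attached to these safety and baseline p-values, and the primary non-inferiority test is unaffected.

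**What to change.** - **Table 14.3.1, yes/no rows:** CMH stratified by the four randomization strata, matching 14.3.2 and 14.3.3, with an exact version when events are sparse. State the strata in the 14.3.2 note too.
- **Severity and causality:** van Elteren (CMH row mean scores with modified ridits), with the category order written in the note.
- **Outcome:** CMH general association, or counts without a p-value. Define the ranking that 8.2.1 needs to pick one outcome per patient.
- **Nominal baseline variables:** CMH general association, or description only.
- **Protocol:** align 12.6.1 and 12.6.5 with 12.1 and the SAP, and drop treatment group from the stratifiers in 12.1.

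The cost is wording and a procedure option in the analysis code. No extra data are needed, and the sample size does not change.
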